7. STUDY DESIGN

We will perform a mixed-methods cohort study to explore the feasibility of EMCAT for measuring between-group differences in postoperative recovery, its potential to guide follow-up type (face-to-face, telemedicine or patient-initiated) in open carpal tunnel decompression, and its potential to guide follow-up timing after steroid injection for TBOA. The study setting will be NHS hospitals in the England, Scotland and Wales.

Our primary objective is to use EMCAT to compare the recovery trajectories of patients undergoing PNF and LF for Dupuytren's disease. We expect to see a difference in recovery trajectory over a 12-week period, with patients undergoing PNF showing less severe symptoms than those undergoing LF over the first 4 weeks. To meet this objective, we will recruit 396 participants (198 undergoing PNF and 198 undergoing LF), who will be followed up for a 12-week period with daily EMCAT assessments.

To address our secondary objectives, we will simultaneously recruit patients undergoing:

- Steroid injection for TBOA
- Steroid injection for trigger finger
- Trapeziectomy for TBOA
- Arthroplasty for TBOA
- Surgical release of trigger finger
- Open CTD
- Minimally invasive (endoscopic or percutaneous) CTD

We will recruit as many participants as we can in these groups, within the limits of the study timing and funding, and up to a maximum of 198 per group. We will use all collected EMCAT data to test the following hypotheses:

- Steroid injection results in less severe post-treatment symptoms than trapeziectomy, within the first 4 weeks
- Trapeziometacarpal arthroplasty results in less severe post-treatment symptoms than trapeziectomy, within the first 4 weeks
- Minimally invasive (endoscopic or percutaneous) CTD results in less severe post-treatment symptoms than open CTD, within the first 2 weeks
- The difference in the recovery of groups undergoing open release vs steroid injection for trigger finger are not clinically significant over the first 2 weeks

The objective is to test EMCAT's ability to differentiate between recovery trajectories that are expected to differ, rather than to prove or disprove that differences in recovery trajectory exist. The clinical comparisons are a vehicle for testing the measurement properties of EMCAT.

Participants undergoing open CTD or steroid injection for TBOA will be automatically entered into a second research stream. Those undergoing steroid injection for TBOA will be followed up with twice weekly EMCAT assessments for a further 12 weeks (24 weeks total). In this stream, participants' medical records will be reviewed by members of the research team at 24 weeks. For patients with TBOA, EMCAT trajectories will be plotted as time series graphs, and follow-up appointment dates will be overlaid onto these plots. They will be inspected to see whether appointments coincide with peaks in symptom severity.

For patients undergoing open CTD, we will record whether the participant underwent any change in management as a result of their follow-up appointment (including but not limited to antibiotic prescription, reoperation, clinical investigation, arrangement of further clinical follow-up and hand therapy referral). We will then ask three independent clinicians to inspect de-identified EMCAT trajectories and predict whether or not the patient required a change in management at their follow up. We will calculate the accuracy of these predictions against what happened to the participant at their follow up.

A subsample of 10 participants recruited from the first and second research streams, and 10 clinicians, will be interviewed about their experiences of the platform. Interviews will follow a schedule that covers the following topics:

- Perceived value of the EMCAT as a data-capture platform
- Acceptability of EMCAT
- Perceived burden of EMCAT
- Facilitators and barriers to using EMCAT
- Areas for improvement within the EMCAT platform

- The potential for EMCAT's to guide follow-up in different scenarios (e.g. open CTD or steroid injections for TBOA)

Participants will be given opportunity to discuss any other aspects of the EMCAT platform they consider important.

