5. Explore whether information provided by the EMCAT platform could have accurately predicted which patients required a change in management during open CTD follow up	Accuracy of independent clinician interpretation of EMCAT trajectories against observed patient management	2 weeks and 12 weeks, or whenever follow- up is timed
6. Explore whether information provided by the EMCAT platform could help to time follow-up appointments for TBOA injections to coincide with patient need	Plots comparing follow-up appointment dates to EMCAT trajectories	Over 24 weeks
7. Explore the patient and clinician perceptions of EMCAT-guided follow-up and clinical monitoring	Semi-structured interviews	

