9.12 Study sequence

- 1. Potential participants will be identified by clinical members of the research team during routine care.
- 2. The clinical team members will invite potential participants to participate on the day of their treatment.
- 3. Potential participants will be provided with a written information pack, and given time to read this and discuss it.
- 4. The investigator will take informed consent from the participant at that point, if the participant feels they have had sufficient time to consider taking part.

- 5. At the point of recruitment, a member of the research team will assist the participant in downloading the EMCAT app and enabling push notifications.
- 6. At the point of recruitment, prior to the treatment, the participant will complete the full-length (11-item) PEM part 2 via the EMCAT app, and a single EMCAT assessment.
- 7. Over the next 12 weeks, participants will complete daily PEM EMCAT questionnaires (if they choose to) when prompted by email or push notification.
- 8. In addition, at 6 and 12 weeks, participants will be asked to complete the full-length PEM part 2 via the app, separately.
- 9. At 12 weeks, participants will also be asked to complete the UES via the app. Participants who do not respond with 7 days will be contacted via email or telephone and asked if they would like to return UES responses either via email or over the telephone. The method of UES response (app/email/telephone) will be recorded, if not via the ECMAT platform.
- 10. At 12 weeks, notifications will stop for all participants except those who underwent steroid injection for TBOA these participants will continue to receive EMCAT notifications twice weekly for a further 12 weeks.
- 11. For participants undergoing steroid injection for TBOA or open CTD, at the 24-week timepoint, a clinical member of the research team will review the participant's medical record and record follow-up appointment dates and (for those who underwent open CTD) whether the follow up resulted in a change of management.
- 12. Three independent clinicians will review de-identified EMCAT trajectories and appointment dates for patients who underwent open CTD, and predict whether each participant required a change in management.
- 13. We will identify and approach 10 patients and 10 clinicians with invitations to take part in semistructured interviews – interviews will take place no later than 14 days after finishing use of the EMCAT platform.

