11.4 Description of the Statistical Methods

The hypotheses outlined in the primary and secondary objectives will be tested with mixed-effects linear modelling. These models will comprise: EMCAT score (continuous dependent variable on a logit scale, derived from a graded response model); participant number (random intercept); age, sex, and baseline score (fixed effects); and an interaction term between time (number of days following the intervention) and treatment allocation. Marginal means will be derived from these models and between-group differences calculated at daily timepoints after Tukey adjustment for multiplicity. This will be performed with the *emmeans* R package, or equivalent software. For each comparison, marginal means will be plotted, and differences compared to a minimal important difference (MID) estimate of half a standard deviation of baseline scores. Clinically and statistically significant (at the 5% level) differences will be compared to those predicted (see section 6).

EMCAT completion rates (number of completed response sets divided by number of invitations), response times, and UES scores will be analysed through descriptive statistics. The UES was originally intended to measure 6 user engagement constructs, but subsequent studies have suggested that it follows a 4-factor structure. Items of the UES will be grouped into the 4 subscales described by O'Brein et al, to measure: focused attention, aesthetic appeal, perceived usability and reward⁵.

The criterion validity of the EMCAT scores against the full-length PEM scores will be assessed by comparing pairs of EMCAT scores and full-length PEM scores that were obtained from the same participant on the same day. Comparison will be made by calculating Pearson's correlation coefficient, mean absolute error, root mean squared error and the Bland-Altman method⁶.

In Stream 2, three independent clinicians will review EMCAT trajectories (presented as time series plots) and follow-up appointment dates for participants that underwent open CTD. They will be asked to predict whether a change in management was required at the follow-up appointment. We will calculate inter-rater reliability of these assessments (Fleiss' kappa) and, for each clinician, the accuracy, sensitivity, specificity, positive predictive value and negative predictive value of their predictions against the reference standard (whether or not the patient received a change in management).

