In Stream 2, for patients who have undergone steroid injection for TBOA or open CTD, a clinical member of the team will access the participants medical record after the 24-week timepoint to record data relating to the exploratory objectives in the site's study data spreadsheet. This includes the timing of follow-up appointments and (for open CTD), whether the patient underwent a change in clinical management (e.g. antibiotic prescription, reoperation or hand therapy referral) during their follow-up. Deidentified study spreadsheets will be securely transferred from the sites to the central research team in line with local policies. These will be stored up on the CI's University of Oxford SharePoint. Deidentified data will be analysed using a password protected personal device that meets NDORMS Mobile Devices policy and accessed via the University VPN to ensure a high level of security. The deidentified study data spreadsheets will be stored for three years on SharePoint. This will be detailed on the PIS.

In Stream 3, semi-structured interviews will be conducted using the Microsoft Teams videoconferencing platform. The audio (but not the video) of these interviews will be recorded onto a password protected personal device that meets NDORMS Mobile Devices policy and accessed via the University VPN to ensure a high level of security, and transcribed verbatim by one of the central researchers. This will be achieved by turning off the video in the meeting prior to recording. Transcripts will be de-identified immediately and then identifiable recordings will be deleted. Deidentified transcripts will be stored on the Cl's University of Oxford SharePoint. They will be stored for three years on the personal device and SharePoint. In order to arrange the timing of these meetings, the names and email addresses of participants recruited to Stream 3 will be securely transferred to the central research team. This will be detailed on the Stream 3 consent forms.

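### The open carpal tunnel reference standard does not exclude routine follow-up or therapy and sets no limit on the appointment date, so the accuracy figures would partly reflect booking practice

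*Protocol*

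**What the plan says.** Objective 5 (section 6, exploratory) asks whether EMCAT information "could have accurately predicted which patients required a change in management during open CTD follow up". Its timepoints are given as "2 weeks and 12 weeks, or whenever" follow-up takes place.

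Section 7 has the research team record "whether the participant underwent any change in management as a result of their follow-up appointment", and illustrates this with an open list: "including but not limited to antibiotic prescription, reoperation, clinical investigation, arrangement of further clinical follow-up and hand therapy referral". Section 12.5, on what sites enter in the study spreadsheet, has them note "whether the patient underwent a change in clinical management (e.g. antibiotic prescription, reoperation or hand therapy referral) during their follow-up". Section 11.4 takes as reference standard "whether or not the patient received a change in management", with no further definition. From it, section 11.4 derives accuracy, sensitivity, specificity, PPV and NPV for each of three clinicians, who see the trajectory and the appointment dates.

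On timing, section 9.12 states: "At 12 weeks, notifications will stop for all participants except those who underwent steroid injection for TBOA". Sections 7, 9.12 and 12.5 place the medical record review for open CTD at 24 weeks.

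Section 11.3 says that no separate SAP is in use, and section 12 says the same of a data management document. The definition is therefore fixed here.

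**The concern.** Section 7 gives the use of this analysis as guiding the type of follow-up after open CTD. The lay summary asks whether a clinic visit could have been avoided. A label suited to that question should separate patients who needed something done from those who did not.

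The label as written does not do so cleanly, for two reasons.

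- **Content.** Arranging another appointment and referring to hand therapy are both listed as changes. Nothing separates a visit or referral that most patients receive from one prompted by a problem. With a 2-week and a 12-week visit expected, a patient recovering normally whose 12-week visit is booked at the 2-week clinic can be recorded as positive. That is the patient EMCAT is meant to identify as not needing to be seen.
- **Timing.** The appointment date has no upper limit. A visit at week 18, for example, could enter the reference standard although the last scheduled EMCAT prompt was six weeks before.

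In both cases a rater who reads the trajectory correctly can be scored wrong. NPV, the figure most relevant to deciding who need not be seen, is among those affected. If routine and unplanned follow-up are not separated when the records are read, the accuracy figures cannot be repaired later without repeating the review.

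**Working it through.** The protocol states no sensitivity, NPV, prevalence or target for this analysis, so there is no figure to reproduce. The check asks how far the label could move the results. All rates below are assumptions.

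**Inputs**
- *t*: share of patients who truly need a change. Assumed 10%, range 5% to 20%.
- *q*: share of the remaining patients labelled positive only through routine rebooking or referral, independently of symptoms. Assumed 25%, 50% or 75%.
- Maximum open CTD group: 198 (section 7).

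**Step 1: a rater who is perfect on true need**

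Labelled prevalence P = t + (1 − t)q. Sensitivity = t / P. NPV = (1 − P) / (1 − t). Accuracy = t + (1 − P).

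With t = 10%:

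| q | P | Sensitivity | NPV | Accuracy |
|---|---|---|---|---|
| 25% | 0.10 + 0.90 × 0.25 = 0.325 | 0.10/0.325 = 31% | 0.675/0.90 = 75% | 78% |
| 50% | 0.10 + 0.90 × 0.50 = 0.550 | 0.10/0.550 = 18% | 0.450/0.90 = 50% | 55% |
| 75% | 0.10 + 0.90 × 0.75 = 0.775 | 0.10/0.775 = 13% | 0.225/0.90 = 25% | 33% |

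At q = 50%, sensitivity is 0.05/0.525 = 10% for t = 5% and 0.20/0.60 = 33% for t = 20%. NPV reduces to 1 − q whatever the value of t. Specificity and PPV stay at 100% for this rater: every labelled negative is a true negative, and every patient called positive is labelled positive.

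**Step 2: an imperfect rater**

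Take sensitivity and specificity of 0.80 against true need, t = 10% and q = 30%. Shares of all patients:
- Labelled positive, called positive: 0.10 × 0.80 + 0.27 × 0.20 = 0.134
- Labelled positive, called negative: 0.10 × 0.20 + 0.27 × 0.80 = 0.236
- Labelled negative, called positive: 0.63 × 0.20 = 0.126
- Labelled negative, called negative: 0.63 × 0.80 = 0.504

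| Measure | Routine follow-up excluded (q = 0) | Counted (q = 30%) |
|---|---|---|
| Sensitivity | 0.80 | 0.134/0.370 = 0.36 |
| Specificity | 0.80 | 0.504/0.630 = 0.80 |
| PPV | 0.08/0.26 = 0.31 | 0.134/0.260 = 0.52 |
| NPV | 0.72/0.74 = 0.97 | 0.504/0.740 = 0.68 |
| Accuracy | 0.80 | 0.134 + 0.504 = 0.64 |

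Of 198 participants, labelled positives rise from 198 × 0.10 ≈ 20 to 198 × 0.37 ≈ 73. At q = 30%, sensitivity is 0.29 for t = 5% and 0.47 for t = 20%.

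**Step 3: late appointments**

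Keep this rater with t = 10% and q = 0. Suppose 25% of true need arises after week 12 and is called positive only at the false-positive rate of 0.20. Sensitivity is then 0.75 × 0.80 + 0.25 × 0.20 = 0.65, and NPV is 0.72/(0.72 + 0.035) = 0.95. Specificity stays at 0.80. Under these assumptions, timing has a smaller effect than routine rebooking.

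**The case against.** The strongest reply is that the bracketed list illustrates a governing phrase: the change must come about as a result of the appointment. A 12-week visit already in the pathway is not naturally a change, nor a product of the 2-week visit. That reading is available, so a reader should not infer that the protocol positively counts routine rebooking. But a 12-week visit booked at the 2-week clinic is also arranged as a result of that clinic, and nothing tells the staff reading the notes which view to take. What stands is that routine follow-up is not excluded.

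Other stronger readings also fail:

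- **A 24-week outcome window.** Week 24 is when records are opened. Objective 5 names 2 and 12 weeks or whenever follow-up falls. The defect is a missing upper limit, and how often late visits occur is unknown.
- **A contradiction between sections 7 and 12.5.** Both lists are marked as illustrative, and the shorter is contained in the longer. They leave room for differing labels but do not conflict.
- **Distorted specificity.** It is unchanged in both steps above when rebooking is independent of the trajectory.
- **Figures that show booking practice instead of need.** The label mixes the two. If clinicians mainly rebook patients who recover poorly, the loss is smaller than shown. For the perfect rater to miss most labelled positives, q must exceed t/(1 − t), about 11% at t = 10%.

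A broad standard is also partly defensible: a patient whose clinician decided on another review arguably needed attention. That supports reporting the broad definition, but not using it alone.

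**Conclusion.** The point holds as a gap in the definition. Follow-up and therapy that are routine are not excluded from the reference standard, and appointments have no latest date although open CTD EMCAT ends at week 12. Sensitivity, NPV and accuracy would partly reflect booking practice, as would PPV for any rater who makes false-positive calls.

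The size cannot be known from the protocol. The illustrated falls, to sensitivity 31% to 13% and NPV 75% to 25% for a rater perfect on true need, rest on an assumed 10% need, an assumed 25% to 75% routine rebooking or referral, and independence of rebooking from symptoms. The objective is exploratory, with no hypothesis test or accuracy target attached, so severity is modest. The case for acting is that the remedy is cheap now and difficult after the records have been read.

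**What to change.** 1. Use one definition of a change in management in sections 7, 9.12, 11.4 and 12.5.
2. At the record review already planned, enter routine or already planned follow-up and therapy in a separate field from unplanned actions.
3. Take unplanned actions as the main reference standard, and report accuracy under the broad definition beside it. Showing both matters because what is routine differs between sites, so a label resting only on each site's own pathway would be site-dependent.
4. Restrict the main analysis to appointments covered by the EMCAT period, with a short stated window so that a slightly late 12-week visit is kept. Report later appointments separately.

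The cost is protocol wording and one extra spreadsheet column; patient care does not change. The downside is fewer labelled positives, so wider intervals on sensitivity. In the illustration at 10% need and 30% rebooking, about 20 of 198 would be positive instead of about 73.

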8. PARTICIPANT IDENTIFICATION

8.1. Study Participants

Adults undergoing one of the eligible treatments at a participating NHS Trust. Eligible treatments are:

- PNF for Dupuytren's contracture
- LF for Dupuytren's contracture
- Steroid injection for TBOA
- Trapeziectomy for TBOA
- Arthroplasty for TBOA
- Open CTD
- Minimally invasive (e.g. percutaneous or endoscopic CTD)
- Open trigger finger release
- Steroid injection for trigger finger

8.2. Inclusion Criteria

- Participant is willing and able to give informed consent for participation in the study
- Participant is aged 18 years or older
- Participant is going to undergo one of the eligible treatments
- Participant is willing and able to download and engage with the EMCAT application on their own personal device

8.3. Exclusion Criteria

- Participant is undergoing bilateral treatments

Clinical Research Protocol Template version 15.0

- Multiple treatments to the affected hand (for any condition) are planned within the study period
- Participant is unable to engage with the EMCAT application in the English language

8.4. Welsh Language Act

In line with the Welsh Language Act 1993 all clinical appointments in Wales have to be available in Welsh. Neither the PEM questionnaire nor the UES have been item response theory validated in the Welsh language versions. Only the English version of the PEM can be administered in the adaptive manner required by EMCAT. For the purposes of this study, we consider the lack of a validated Welsh language versions to be a reasonable exclusion criteria for potential participants unable to comprehend the English language.

9. PROTOCOL PROCEDURES

9.1. Recruitment

Eligible participants will be identified by clinical members of the research team who have routine access to the data which will be used to identify potentially eligible participants. Prior to the patient's treatment, a member of the research team will discuss the study with them and invite them to partake. Written information will be provided to the potential participant, and they will be offered time alone to read the material and consider taking part. It will be made explicitly clear that participants are free to decline without reason, and this will not affect the care they receive in future. We anticipate that most people will be able to make an informed and considered decision about taking part on the same day as their appointment. If participants are unable to make a decision on the day of their appointment, they will be unable to participate.

If the participant accepts the invitation, written consent will be taken. Participants will be provided with a research team member's email address, and are free to withdraw consent at any time by emailing them as well as by contacting the study team by phone or email, or during the face to face appointments (see section 9.3 for caveats).

Participants undergoing open carpal tunnel decompression or steroid injection for TBOA will be included in Streams 1 and 2, with details provided in the participant information material. We will seek consent to contact participants at a later date for recruitment to Stream 3.

Participants who have consented to be contacted about Stream 3 may either be called or emailed with an invitation to take part in the qualitative interviewing (Stream 3). They will be provided with written information and given time to consider their involvement. Separate remote consent will be taken for involvement in the interviews (see section 9.3).

